### 2. Abstract

**Objective:** Difficulty retrieving words, one of the most common language complaints in healthy older adults and those with mild cognitive impairment (MCI) stroke-induced language disorders (i.e., aphasia), can have a negative impact on communicative function. Consistent with studies in young adults, our pilot study in healthy older adults, demonstrates that acute exercise may improve word learning; however, more research is needed to optimize learning paradigms for healthy older adults and those with MCI and aphasia and to investigate the factors that contribute to exercise-induced improvements in learning in these populations. The objectives of this research are to: 1) identify an optimal novel word learning paradigm; 2) determine the acute effects of exercise (compared to stretching) on word learning; 3) investigate the influence of timing of exercise (exercise before vs. after learning); 4) investigate the influence of high vs. low working memory ability on exercise-enhanced word learning; and 5) investigate the neurophysiological correlates of exercise-enhanced word learning.

**Research Plan:** Word learning performance will be compared in up to four conditions (before exercise, after exercise, before stretching, after stretching). Performance of individuals with high vs. low working memory will be compared and peripheral levels of brain-derived neurotrophic factor (BDNF) and dopamine will be measured to investigate correlates of immediate and one-week retention of learned words.

**Methods:** We will compare word learning in up to four conditions using a within-subjects crossover design. Individuals aged 65-89 years (healthy older adults and MCI) and 35-89 years (individuals with aphasia) who meet the eligibility criteria will be offered enrollment. In the exercise conditions, participants will engage in 30 minutes of moderate-intensity cycling (with a warm-up/cool-down) before or after word learning. In the stretching conditions, participants will engage in upper- and lower-limb stretching for 30 minutes before or after word learning. In the word learning task, participants will be asked to learn novel words ("flark") for a familiar object ("cup") and will engage in tests of recall and recognition. Each condition will last two weeks. In week 1, training /testing will take place on Monday, Wednesday and Friday of week 1 to measure immediate retention. In week 2, testing will take place on Friday to measure one-week retention. To measure serum levels of BDNF and dopamine, blood samples will be taken at baseline (every 15 minutes for one hour) and in the two training conditions when exercise/stretching occurs before word learning (immediately before exercise/stretching, immediately after exercise/stretching, immediately after word learning, and 15 minutes after word learning).

**Clinical Relevance:** The aging population of the US is expected to more than double by 2060, and a similar trajectory is expected within our aging veteran population.

Additionally, stroke affects 795,000 individuals per year, and up to 30% are left with chronic disability including language impairment. MCI can also have an impact across all cognitive domains, including language and memory (Arnaiz & Almkvist, 2003). The declines in communicative function that are present in healthy older adults and those with aphasia often result in reduced independence and psychosocial well-being, and they may contribute to poorer health outcomes. Investigating an exercise-based approach to improving word retrieval is clinically relevant and has the potential to have a significant impact on the functioning and well-being of thousands of aging veterans.

### 3. Introduction and Background

The onset of cognitive decline can begin before 30 years of age (Salthouse, 2004), but the potential for improving brain function remains throughout the lifespan. To combat the effects of aging on cognition, exercise-based programs aimed at taking advantage of reactive neuroplasticity (immediate, short term changes) to promote adaptational neuroplasticity (long term changes) have become increasingly popular. Engaging in physical exercise promotes neuroplasticity through increased cerebral blood flow, increased neurogenesis, and neurochemical release (Greenwood & Parasuraman, 2010). Meta-analyses have shown that acute exercise has small to moderate effects on working memory (McMorris et al., 2012; Roig et al., 2013) and large effects on long-term memory (Roig et al., 2013; Lambourne & Tomporowski, 2010).

Difficulty retrieving the right word at the right time is one of the most common complaints in healthy older adults and those with MCI and stroke-induced language impairment (i.e., aphasia). The consequences of word retrieval deficits include reduced independence and psychological well-being (Llewellyn et al., 2008) as well as poor health outcomes. Novel word learning paradigms have been used to investigate a variety of behavioral and neuromodulatory approaches to word retrieval deficits in these populations. We are using a novel word learning paradigm to investigate the acute (or immediate) effects of exercise on word recall with a long-term goal of developing targeted interventions for word retrieval impairment. In a pilot study, we demonstrated that engaging in moderate-intensity exercise can improve long-term *recognition* of novel words (e.g., flark) for familiar objects (e.g., ball) in healthy older adults ([name] et al, in prep); however, evidence regarding acute exercise effects on novel word *recall* and the potential mechanisms that support these effects is required.

Moreover, despite the known declines in language, learning and working memory in the aging population, no studies have investigated the influence of baseline working memory ability on exercise-enhanced word learning. Additionally, other factors, such the influence of timing of exercise in relation to learning have also not been investigated in older adults. As not all cognitive functions are likely to be enhanced by exercise (Lambourne & Tomporowsk, 2010; Roig et al., 2013), and individual differences in baseline cognitive function have been shown to influence outcomes in younger adults (Sibley & Beilock, 2007; Schmidt-Kassow et al. 2013), this line of inquiry is an important step in developing effective exercise-based interventions.

Similarly, there has also been very little research on the neural correlates of exercise-enhanced word learning, and the results of two studies in younger adults yielded contrasting results. Winter and colleagues (2007) found that increased levels of serum brain-derived neurotrophic factor (BDNF) and dopamine were related to short- and long-term learning success (respectively) in young male athletes who engaged in high intensity prior to learning; however, Schmidt-Kassow et al (2013) failed to find a link between serum BDNF and learning in healthy young females who engaged in light to moderate exercise during learning. Although a recent review by Coelho and colleagues (2013) suggests that moderate-intensity exercise is most effective in promoting increased BDNF levels in the elderly, no studies have investigated the relationship between BDNF and word learning in aging populations.

Our research aims to address these gaps in the literature in order to inform the development of targeted, exercise-based interventions for word retrieval impairments in healthy older adults and those with stroke-induced aphasia.

### **3. Objectives/Hypothesis/Research Questions**

- 1) To identify an optimal novel word learning paradigm for investigation of acute exercise effects on word recall
- 2) To determine the effect of moderate-intensity aerobic exercise (compared to a stretching control) on word learning
- 3) To investigate factors known to modulate acute exercise effects such as:
  - a. Timing of exercise (exercise before vs. after learning)
  - b. Individual differences (high vs. low working memory ability)
- 4) To investigate the neurophysiological correlates of exercise-enhanced word learning

*Research Question 1:* Does acute, moderate-intensity exercise (compared to gentle stretching) enhance novel word learning in healthy older adult and neurologic populations? Based on our pilot work, we hypothesize that with an optimal paradigm both recall and recognition will be significantly better in the moderate-intensity exercise condition (compared to gentle stretching).

#### *Research Question 2: Modulating Factors*

- a. Does timing of exercise in relation to word learning moderate the effect of acute exercise on novel word learning in healthy older adults and individuals with MCI or aphasia?
- b. Do individual differences in baseline working memory moderate the effect of acute exercise on novel word learning in healthy older adults and individuals with MCI or aphasia?

Based on our pilot data, the findings that acute exercise benefits low performers at baseline (Schmidt-Kassow et al., 2013; Sibley and Beilock; 2007), and the findings that acute exercise improves processing efficiency (McMorris et al., 2012), we hypothesize

that exercise (compared to gentle stretching) before learning will significantly enhance immediate and long-term retention of words in the low working memory group (compared to the high working memory group). Furthermore, based on findings that exercise improves long-term retention ([name] et al., in prep; Roig et al., 2013), we hypothesize that exercise (compared to gentle stretching) after learning will significantly enhance long-term retention of words (compared to immediate retention) with no significant difference in the change between the high and low working memory groups.

*Research Question 3:* Does exercise-enhanced novel word learning correlate with increases in peripheral levels of BDNF or dopamine in healthy older adult and individuals with MCI or aphasia? Based on previous exercise and word learning research, we hypothesize that significantly better short-term retention (immediately after learning) will correlate with increased BDNF levels and that significantly better long-term retention (at one-week follow-up) will correlate with increased levels of dopamine.

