#### **6. Overview of Design/Methods**

The study will enroll up to 100 healthy older adults and up to 50 older adults with MCI and stroke-induced aphasia. A crossover design will be used to compare two novel word learning paradigms and/or the additive effect of moderate-intensity exercise vs. stretching on novel word learning.

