##### *Study procedures*

##### Assessment:

The subject's cognitive and physical function will be assessed at the start of the study. Some assessments may be audio-recorded for scoring and reliability assessment.

Cognitive Assessment:

- a) Reading Span (RSPAN) and Operation Span (OSPA): assesses working memory capacity. These two tests will allow us to categorize subjects into high vs low working memory, which will allow us investigate how acute exercise effects vary as a function of individual differences in baseline working memory ability (Objective 3b).
- b) Digit Span: assesses the central executive component of working memory
- c) Verbal fluency (semantic and letter): assesses the verbal component of executive function
- d) Color-word Interference Test: assesses the inhibition component of executive function
- e) Hopkins Verbal Learning Test: assesses verbal learning and memory (immediate recall, delayed recall, delayed recognition)
- f) Brief Visuospatial Memory Test- Revised: assesses visuospatial memory (immediate recall, delayed recall, delayed recognition)
- g) Digit Symbol Substitution: sensitive to the effect of brain damage, dementia, age and depression on task completion
- h) American National Adult Reading Test- Revised: estimates intelligence in based on reading of words with irregular grapheme-to-phoneme conversion.
- i) Edinburgh Handedness Inventory: assesses handedness
- j) *Task practice:* Subjects will be administered a practice word learning task at baseline to familiarize them with the novel word learning paradigm.
- k) Discourse production: Subjects will be asked to answer two open-ended questions in order to get a measure of their connected speech.

The following measures will be administered to participants with aphasia:

- a) Comprehensive Aphasia Test- assesses general language ability
- b) Philadelphia Naming Test- assesses confrontation naming ability
- c) Pyramids and Palm Trees- assesses semantic processing ability

Physical Assessment:

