Official Study Title:

Acute Exercise Effects on Word Learning in Aging and Stroke-induced Aphasia

NCT# 03370471

Document Date: 09/16/19

Statistical Analysis Plan

The following analyses apply to data from healthy adult participants who completed the study:

Primary Outcome

Aim 1. We will use a mixed effects model approach to fit repeated measures ANOVAs to word recall scores obtained at three time points: 1) after learning (acquisition), 2) immediately before exercise or stretching on two days (consolidation), and one week after the final learning session (long-term recall).

Secondary Outcome

Aim 2. We will use a mixed effects model approach to fit repeated measures ANOVA to serum BDNF concentration levels (pg/mL) obtained at four time points: 1) before exercise or stretching, 2) immediately after exercise or stretching, 3) immediately after learning, and 4) 15 minutes after learning.

Post-hoc Analysis:

We will use a mixed effects model approach to fit repeated measures ANOVAs to word recognition scores obtained at three time points: 1) after learning (acquisition), 2) immediately before exercise or stretching on two days (consolidation), and one week after the final learning session (long-term recall).

The following analyses apply to data from participants with aphasia who completed the study:

Primary Outcome

Aim 1. We will calculate gains for word recall at three time points: 1) after learning (acquisition), 2) immediately before exercise or stretching on two days (consolidation), and one week after the final learning session (long-term recall).

Secondary Outcome

Aim 2. We calculate means of serum BDNF concentration level (pg/mL) obtained at four time points: 1) before exercise or stretching, 2) immediately after exercise or stretching, 3) immediately after learning, and 4) 15 minutes after learning.

Post-hoc Analysis:

We will calculate gain scores at three time points: 1) after learning (acquisition), 2) immediately before exercise or stretching on two days (consolidation), and one week after the final learning session (long-term recall).

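### Research Question 2's no-difference clause for exercise after learning would be met by a non-significant test, which cannot show that the working-memory groups respond alike

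*Protocol*

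**What the plan says.** The protocol, under Research Question 2 (Modulating Factors), makes two predictions about working memory.

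- Exercise before learning: the prediction is a difference. Exercise "before learning will significantly enhance immediate and long-term retention of words in the low working memory group", compared with the high group.
- Exercise after learning: the prediction has two parts. Long-term retention should improve significantly relative to immediate retention, and this should happen "with no significant difference in the change between the high and low working memory groups".

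The groups come from the Reading Span and Operation Span tests (protocol Section 6, Cognitive Assessment): "These two tests will allow us to categorize subjects into high vs low working memory". No cut-off or group size is given. On numbers, Section 6 says only: "The study will enroll up to 100 healthy older adults and up to 50 older adults with MCI and stroke-induced aphasia". These are ceilings, not a calculated sample size.

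The SAP does not mention working memory. For healthy adults it says: "We will use a mixed effects model approach to fit repeated measures ANOVAs to word recall scores obtained at three time points". For aphasia it says: "We will calculate gains for word recall at three time points", with no test named. Neither document states a significance level, a power or an equivalence margin.

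**The concern.** The after-learning clause predicts the outcome of a significance test, not the size of a difference. Failing to reach significance is compatible with no difference, with a small one, and with a moderate one that the study could not detect. Nothing in the wording separates these.

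Working-memory moderation is a stated aim (Objective 3b), and Research Question 2 sets up a contrast: moderated by working memory when exercise comes first, not moderated when it comes afterwards. The second half of that contrast would rest on an unrejected null hypothesis in a between-subject comparison. A conclusion that post-learning exercise works whatever a person's working memory could then affect whom later interventions target.

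This is distinct from the missing working-memory analysis in the SAP. Adding an interaction test would fill that gap but would leave the no-significant-difference wording as the standard for success.

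**Working it through.** There is no figure in the plan to reproduce, so the calculation is illustrative.

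**Inputs.** From the documents: at most 100 healthy older adults, so 50 per group if split equally. Assumed: equal groups; two-sided 5% test; each person contributes one exercise-minus-stretching change; the true group difference d is expressed in SDs of that change; 20 per group stands for a smaller study.

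**Step 1: chance of a non-significant result when a real difference exists.** For a two-sample t-test with n per group, the noncentrality is d × √(n/2), the degrees of freedom are 2n − 2, and P(non-significant) = 1 − power.

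| n per group | d | noncentrality | power | P(non-significant) |
|---|---|---|---|---|
| 50 | 0.3 | 0.3 × 5 = 1.50 | 0.32 | 68% |
| 50 | 0.5 | 0.5 × 5 = 2.50 | 0.70 | 30% |
| 20 | 0.3 | 0.3 × 3.16 = 0.95 | 0.15 | 85% |
| 20 | 0.5 | 0.5 × 3.16 = 1.58 | 0.34 | 66% |

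A normal approximation gives 67.7%, 29.5%, 84.2% and 64.7%. If d is exactly 0, the result is non-significant 95% of the time at every n.

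**Step 2: the whole hypothesis, not just the clause.** The hypothesis also needs a significant mean enhancement. Assume a mean effect of 0.5 SD and a real group difference of 0.5 SD. With equal groups the two results are independent, so under the normal approximation the joint probability is Φ(0.5 × √(2n) − 1.96) × P(non-significant).

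- n = 50: 0.999 × 0.295 = 29%
- n = 25: 0.942 × 0.576 = 54%
- n = 10: 0.609 × 0.799 = 49%
- n = 5: 0.352 × 0.876 = 31%

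The probability rises and then falls as n shrinks.

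**Step 3: what an interval could show.** The 90% CI half-width is t(0.95; 2n − 2) × √(2/n).

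- n = 50: 1.66 × 0.200 = 0.33 SD
- n = 20: 1.69 × 0.316 = 0.53 SD

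With 20 per group, an observed difference of exactly zero would still leave a difference of about half an SD in either direction inside the interval. The clause would nevertheless count as met.

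**The case against.** The strongest reply is that this is a prediction in an objectives section, not a decision rule. No document says that p > 0.05 will be taken as proof of similarity, and the SAP plans no working-memory test, so the error might never be made. This stands in part: the flaw lies in the protocol's hypothesis, and its effect depends on an analysis that is not yet planned. It does not remove the point, because the clause is the only stated standard for this comparison and would naturally be carried over if the analysis were added.

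A second reply is that the after-learning condition may not be run. The abstract allows up to four conditions, Section 6 lets the exercise or stretching come before learning, after it or both, and the Section 7 timeline lists one exercise and one stretching condition without committing to an after-learning arm. This stands, and the fix is conditional on it.

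Three stronger readings are tempting, and the documents do not support them.

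- A reader might infer that the smaller or noisier the study, the more likely the hypothesis is to be confirmed. That holds only for the no-difference clause, and only when a real difference exists. The significant-enhancement requirement pulls the other way (Step 2).
- A reader might infer that a small to moderate difference would usually be missed. At 0.5 SD with 50 per group it is missed in about 30% of studies.
- A reader might infer that this is the study's weakest comparison. No power is stated for any comparison, and others, such as the biomarker correlations in a subset of subjects, could be weaker.

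**Conclusion.** The point holds for one clause. A non-significant between-group test would satisfy the no-difference prediction for exercise after learning, and such a test cannot establish that the working-memory groups respond alike.

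The illustrative miss rates range from about 30% (0.5 SD, 50 per group) to about 85% (0.3 SD, 20 per group). They rest on assumed equal groups, a two-sided 5% test and assumed effect sizes. The 50-per-group case also takes the enrolment ceiling as reached with every participant completing; the SAP analyses completers only, so actual numbers could be lower.

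The point concerns a modulating-factor hypothesis and does not affect the primary outcome analysis.

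**What to change.** If the after-learning condition is run, replace the clause with wording such as: *We will estimate the high-minus-low working-memory difference in the exercise-minus-stretching change, with a 95% CI, and will not conclude that the groups are similar from a non-significant test.* Add the same estimate to the SAP.

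If the sponsor wants to claim similarity, it should justify a margin in advance and otherwise report the result as inconclusive. That may be hard to achieve. Take ±0.5 SD purely as an example margin, with a true difference of zero and two one-sided 5% tests: the power is about 61% with 50 per group and 10% with 25 per group.

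The cost is one sentence in the protocol, plus a working-memory term and a grouping rule in the SAP, which has neither now. No new visits or data are needed, because the span tests are already collected at baseline. The downside is that a conclusion of benefit regardless of working memory becomes harder to support.

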#### **4. Description of Relevance to VA**

It is anticipated that by 2060 the aging population in the United States will more than double to 92 million (United States Census Bureau, 2012). A similar trajectory is expected within our aging veteran population over the next decade. Aging can significantly impact cognitive functions including language, learning and memory (Burke & Mackay, 1997). Difficulty retrieving words is one of the most common complaints in healthy older adults and individuals with MCI and stroke-induced aphasia. Consequences of word retrieval deficits include reduced independence and psychosocial well-being (Llewellyn et al., 2008), as well as poor health outcomes. Safe, cost-effective, accessible approaches for enhancing word retrieval in older adult populations are needed. Exercise is one approach that has yielded positive effects on the ability to remember new words, but more research is required so that exercise-based interventions for word retrieval can be optimized. That is the focus of this line of research. Due to the pervasiveness of word retrieval difficulty in aging populations, and the negative consequences associate with it, this research has the potential to significantly impact veterans in our rapidly aging nation.

#### **6. Overview of Design/Methods**

The study will enroll up to 100 healthy older adults and up to 50 older adults with MCI and stroke-induced aphasia. A crossover design will be used to compare two novel word learning paradigms and/or the additive effect of moderate-intensity exercise vs. stretching on novel word learning.

